4.2.2.3. Laboratory assessments - any time during study day

- If clinically indicated, obtain blood samples for CBC with differential and chemistry panel (see Laboratory Manual)
- If blood gases are available, calculate BE
- If clinically indicated, obtain CRP and serum procalcitonin levels
- If clinically indicated, perform urinalysis (see Laboratory Manual)
- Calculate urine output over the last 8-hour period
- If clinically indicated and performed as part of patient's regular medical care, obtain CSF sample.

4.2.2.4. PK procedures

- Do not draw PK blood samples if the patient received a blood or blood component transfusion within the past 24 hours. For patients who are at risk from additional blood loss, collection of PK samples will require assessment by the investigator.

- Obtain 2 PK blood samples after any infusion of ceftaroline fosamil, between the end of the fourth infusion and before EOT or Study Day 14 (whichever is earlier), according to the patient's assigned PK schedule shown below:

PK Schedule 1	At the end of the ceftaroline fosamil infusion (\pm 5 minutes)
	3 to 4 hours after the end of the infusion
PK Schedule 2	15 minutes to 2 hours after the end of the ceftaroline fosamil infusion
	5 to 7 hours after the end of the infusion (before the start of the next infusion)

- If a lumbar puncture (or other CSF sample collection) is expected and the 2 PK blood samples have not been collected, the time of one of the PK blood samples should be adjusted to correspond to the time of the lumbar puncture; the total number of PK blood samples collected will not exceed 2.
- After the 2 PK blood samples have been collected, any portion of a CSF sample (collected as part of standard of care) not required for the patient's medical care should be retained for PK analysis.

4.2.2.5. Microbiological assessments - any time during study day

- If clinically indicated and performed as part of patient's regular medical care, obtain blood and urine samples for testing per [Section 5.2.1](#) and [5.2.2](#), respectively; cultures should be repeated per standard of care upon knowledge of a positive result until sterilization is confirmed.
- If clinically indicated and performed as part of patient's regular medical care, obtain CSF or other specimens/tissue samples per [Section 5.2.3](#) and [5.2.4](#), respectively; cultures may be repeated per standard of care upon knowledge of a positive result.

4.2.3. Study Day 3 (starts 48 hours after onset of study drug administration)

4.2.3.1. Study therapy administration

- Ceftaroline fosamil, IV: 6 mg/kg IV over 60 (\pm 10) minutes q8h (\pm 1 hour). The dose should be calculated based on the patient's first weight of the day.
- Ampicillin, IV: dosage per institutional guidelines (after 48 hours, the duration of treatment with ampicillin is at the discretion of the investigator)
- Optional aminoglycoside, IV: choice of aminoglycoside and dosage per institutional guidelines and investigator's judgment. Gentamicin is preferred.

4.2.3.2. Clinical assessments - any time during study day

- Identify, assess, and record any new or ongoing AEs and SAEs
- Record concomitant medications ([Section 7.7](#)). For patients who are being breast fed, record all medications taken by the lactating mother
- Record the findings of a complete physical examination, including, but not limited to, physical findings of LOS, presence of central venous catheter or other medical devices (if applicable)
- Record the patient's first weight of the day
- Record vital signs (heart rate/pulse, blood pressure, respiratory rate, temperature) and oxygen saturation; record highest and lowest daily temperature measurements
- Record adjunctive therapeutic procedures (eg, drainage of foci of infection), if performed
- If clinically indicated, obtain results of CXR, CT scan, or other imaging tests performed as part of the patient's regular medical care.

4.2.3.3. Laboratory assessments - any time during study day

- If clinically indicated, obtain blood samples for CBC with differential and chemistry panel (see Laboratory Manual)
- If blood gases are available, calculate BE
- If clinically indicated, obtain CRP and serum procalcitonin levels
- If clinically indicated, perform urinalysis (see Laboratory Manual)
- Calculate urine output over the last 8-hour period
- If clinically indicated and performed as part of patient's regular medical care, obtain CSF sample.

4.2.3.4. Microbiological assessments - any time during study day

- If clinically indicated and performed as part of patient's regular medical care, obtain blood and urine samples for testing per [Section 5.2.1](#) and [5.2.2](#), respectively; cultures should be repeated per standard of care upon knowledge of a positive result until sterilization is confirmed

- If clinically indicated and performed as part of patient's regular medical care, obtain CSF or other specimens/tissue samples per [Section 5.2.3](#) and [5.2.4](#), respectively; cultures may be repeated per standard of care upon knowledge of a positive result.

4.2.3.5. PK procedures

- Do not draw PK blood samples if the patient received a blood or blood component transfusion within the past 24 hours. For patients who are at risk from additional blood loss, collection of PK samples will require assessment by the investigator.
- If not previously collected, obtain 2 PK blood samples after any infusion of ceftaroline fosamil, between the end of the fourth infusion and before EOT or Study Day 14 (whichever is earlier), according to the patient's assigned PK schedule (see [Section 4.2.2.4](#) for schedule and adjustment for CSF sample collection).

4.2.4. Study Days 4 through 14 (starts 72 hours after onset of study drug administration and an extra 24 hours for each day thereafter)

4.2.4.1. Study therapy administration

- Ceftaroline fosamil, IV: 6 mg/kg IV over 60 (\pm 10) minutes q8h (\pm 1 hour). The dose should be calculated based on the patient's first weight of the day.
- Ampicillin, IV: dosage per institutional guidelines (after 48 hours, the duration of treatment with ampicillin is at the discretion of the investigator)
- Optional aminoglycoside, IV: choice of aminoglycoside and dosage per institutional guidelines and investigator's judgment. Gentamicin is preferred.

4.2.4.2. Clinical assessments - any time during study day

- Identify, assess, and record any new or ongoing AEs and SAEs
- Record concomitant medications ([Section 7.7](#)). For patients who are being breast fed, record all medications taken by the lactating mother
- Record the findings of a complete physical examination, including, but not limited to, physical findings of LOS, presence of central venous catheter or other medical devices (if applicable)
- Record the patient's first weight of the day, daily
- Record vital signs (heart rate/pulse, blood pressure, respiratory rate, temperature) and oxygen saturation; record highest and lowest daily temperature measurements
- Record adjunctive therapeutic procedures (eg, drainage of foci of infection), if performed

- If clinically indicated, obtain results of CXR, CT scan, or other imaging test performed as part of the patient's regular medical care.

4.2.4.3. Laboratory assessments - any time during study day

- If clinically indicated, obtain blood samples for CBC with differential and chemistry panel (see Laboratory Manual); recommended to repeat CBC with differential and chemistry panel at least every 7 days
- If blood gases are available, calculate BE
- If clinically indicated, obtain CRP and serum procalcitonin levels
- If clinically indicated, perform urinalysis (see Laboratory Manual) and calculate urine output over the last 8-hour period
- If clinically indicated and performed as part of patient's regular medical care, obtain CSF sample.

4.2.4.4. Microbiological assessments - any time during study day

- If clinically indicated and performed as part of patient's regular medical care, obtain blood and urine samples for testing per [Section 5.2.1](#) and [5.2.2](#), respectively; cultures should be repeated per standard of care upon knowledge of a positive result until sterilization is confirmed
- If clinically indicated and performed as part of patient's regular medical care, obtain CSF or other specimens/tissue samples per [Section 5.2.3](#) and [5.2.4](#), respectively; cultures may be repeated per standard of care upon knowledge of a positive result.

4.2.4.5. PK procedures

- Do not draw PK blood samples if the patient received a blood or blood component transfusion within the past 24 hours. For patients who are at risk from additional blood loss, collection of PK samples will require assessment by the investigator.
- If not previously collected, obtain 2 PK blood samples after any infusion of ceftaroline fosamfil, between the end of the fourth infusion and before EOT or Study Day 14 (whichever is earlier), according to the patient's assigned PK schedule (see [Section 4.2.2.4](#) for schedule and adjustment for CSF sample collection)

4.2.5. End-of-Therapy (EOT)

Conduct EOT assessments within 24 hours after administration of the last dose of study therapy. Conduct the EOT assessments in place of the regular study visit (eg, Study Days 4 to \leq 14) assessments that would have been performed the day of that visit. If applicable, refer to guidance on when to end study therapy in [Section 3.9](#).

If applicable, as study therapy may or may not be given on the same calendar day as EOT assessments, administer study therapy as described in [Section 4.2.4](#).

4.2.5.1. Clinical assessments - after the last dose of study therapy

- Identify, assess, and record any new or ongoing AEs and SAEs
- Record concomitant medications ([Section 7.7](#)). For patients who are being breast fed, record all medications taken by the lactating mother
- Record the findings of a complete physical examination, including, but not limited to, physical findings of LOS; presence of central venous catheter or other medical devices (if applicable)
- Record weight
- Record vital signs (heart rate/pulse, blood pressure, respiratory rate, temperature) and oxygen saturation; record highest and lowest daily temperature measurements
- Assess clinical outcome (per [Table 5, Section 8.4.1](#))
- Record adjunctive therapeutic procedures (eg, drainage of foci of infection), if performed
- If clinically indicated, obtain results of CXR, CT scan, or other imaging test performed as part of the patient's regular medical care.

4.2.5.2. Laboratory assessments - after the last dose of study therapy

- Obtain blood samples for CBC with differential and chemistry panel (see Laboratory Manual)
- If blood gases are available, calculate BE
- If clinically indicated, obtain CRP and serum procalcitonin levels
- Perform urinalysis (see Laboratory Manual)
- If clinically indicated, calculate urinary output over the last 8-hour period
- If clinically indicated and performed as part of patient's regular medical care, obtain CSF sample.

4.2.5.3. Microbiological assessments - after the last dose of study therapy

- If clinically indicated and performed as part of patient's regular medical care, obtain blood and urine samples for testing per [Section 5.2.1](#) and [5.2.2](#), respectively; cultures should be repeated per standard of care upon knowledge of a positive result until sterilization is confirmed
- If clinically indicated and performed as part of patient's regular medical care, obtain CSF or other specimens/tissue samples per [Section 5.2.3](#) and [5.2.4](#), respectively; cultures may be repeated per standard of care upon knowledge of a positive result.

4.3. Follow-up period

Procedures for this period will be performed according to the schedule outlined in the Study Plan ([Table 1](#)) and the following are descriptions of specific requirements for the Follow-up period:

4.3.1. Test-of-Cure (TOC)

Conduct TOC assessments 8 to 15 days after administration of the last dose of study therapy.

4.3.1.1. Clinical assessments

- Identify, assess, and record any new or ongoing AEs and SAEs
- Record concomitant medications ([Section 7.7](#)). For patients who are being breast fed, record all medications taken by the lactating mother
- Record the findings of a complete physical examination, including, but not limited to, physical findings of LOS, presence of central venous catheter or other medical devices (if applicable)
- Record weight
- Record vital signs (heart rate/pulse, blood pressure, respiratory rate, temperature) and oxygen saturation; record highest and lowest daily temperature measurements
- Assess clinical outcome (per [Table 5, Section 8.4.1](#))
- Record adjunctive therapeutic procedures (eg, drainage of foci of infection), if performed
- If clinically indicated, obtain results of CXR, CT scan, or other imaging tests performed as part of the patient's regular medical care; if test was performed after EOT but before TOC, record the latest result.

4.3.1.2. Laboratory assessments

- If clinically indicated, obtain blood samples for CBC with differential and chemistry panel (see Laboratory Manual)
- If clinically indicated, perform urinalysis (see Laboratory Manual)
- If clinically indicated, calculate urinary output over the last 8-hour period
- If clinically indicated and performed as part of patient's regular medical care, obtain CSF sample.

4.3.1.3. Microbiological assessments

- If clinically indicated and performed as part of patient's regular medical care, obtain blood and urine samples for testing per [Section 5.2.1](#) and [5.2.2](#), respectively; cultures should be repeated per standard of care upon knowledge of a positive result until sterilization is confirmed
- If clinically indicated and performed as part of patient's regular medical care, obtain CSF or other specimens/tissue samples per [Section 5.2.3](#) and [5.2.4](#), respectively; cultures may be repeated per standard of care upon knowledge of a positive result.

If a patient was previously assessed as a clinical failure, perform only safety assessments (ie, AEs and SAEs, concomitant medications, weight, vital signs, CBC with differential, chemistry panel).

4.3.2. Safety Follow-Up (SFU)

Conduct SFU assessments, preferably in person, 28 to 35 days after the last dose of study therapy. The SFU may be conducted via telephone for any patient who has not experienced clinical relapse, did not have ongoing AEs or SAEs at TOC, or did not develop AEs or SAEs since TOC. If symptoms of relapse or new AEs or SAEs are noted, or at the discretion of the investigator, the patient should be immediately scheduled for an in-person visit. If a patient was previously assessed as a clinical failure, only safety assessments should be performed.

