3.9. Discontinuation of investigational product

At any time, parent(s) or legally-acceptable representative(s) are free to discontinue the patient from treatment with IP or withdraw the patient from the study (ie, IP and assessments – see [Section 3.10.2](#)), without prejudice to further treatment. Parent(s) or legally-acceptable representative(s) who decide to discontinue a patient from treatment with IP will always be asked about the reason(s) and the presence of any adverse events. If possible, the patient will be seen and assessed by an investigator(s). Adverse events will be followed up until SFU, 28 to 35 days after the last dose of study therapy (See [Section 6](#)). Any AEs that are unresolved at the patient's last AE assessment in the study are followed up by the investigator for as long as medically indicated, but without further recording in the CRF.

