	CXR, CT scan, or other imaging tests ^h					X ^j		
	CBC with differential ⁱ	X		X ^j		X	X ^j	X ^j
	Chemistry panel ⁱ	X		X ^j		X	X ^j	X ^j
	Base excess			X ^j				
	CRP and Procalcitonin ⁱ			X ^j				
	Urinalysis	X		X ^j		X	X ^j	
PK	Urine output	X ^k	X	X	X		X ^j	
	CSF				X ^j			
	Assignment to PK schedule ^l	X						
	PK blood sample ^m				X			
Micro	CSF sample (if collected per standard of care) & matching blood sample ⁿ				X			
	Blood culture				X ^j			
	Urine culture				X ^j			

CSF culture	X ^j				
Other specimen or tissue cultures	X ^j				
Administration of study therapy	X	X	X	X	X

* Study Day 1 will start at the onset of study therapy and will end 24 hours later. Subsequent Study Days are to follow the same pattern.

Abbreviations: AEs=adverse events; CBC=complete blood count; CRP=C-reactive protein; CSF=cerebrospinal fluid; CT=computed tomography; CXR=chest radiograph; EOT=End-of-Therapy; MRI=magnetic resonance imaging; PK=pharmacokinetic; SAEs=serious adverse events; SFU=Safety Follow-up; TOC=Test-of-Cure.

a. Conduct Baseline assessments within 36 hours before first dose of study therapy.
 b. Conduct EOT assessments within 24 hours after the end of last infusion. Study therapy may or may not be given on the same calendar day as EOT assessments; administration should be as for days 4-14.
 c. Conduct TOC assessments 8 to 15 days after the last dose of study therapy.
 d. Conduct SFU assessments, preferably in person, 28 to 35 days after the last dose of study therapy. The SFU may be conducted via telephone for any patient who has not experienced clinical relapse, did not have ongoing AEs or SAEs at TOC, or did not develop AEs or SAEs since TOC. If symptoms of relapse or new AEs or SAEs are noted, or at the discretion of the investigator, the patient should be immediately scheduled for an in-person visit. If the visit is in-person, weight, vital signs and oxygen saturation should be recorded. If a patient was previously assessed as a clinical failure, only safety assessments will be performed.
 e. Refer to the inclusion criteria ([Section 3.1](#)) for the recommended definitions of clinical and laboratory inclusion criteria.
 f. For patients who are being breast fed, record all medications taken by the lactating mother for 3 days before first dose of study therapy through SFU.
 g. Postbaseline, record highest and lowest postdose temperature measurements.

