4.3.2.1. If SFU conducted via telephone

- Record concomitant medications ([Section 7.7](#)). For patients who are being breast fed, record all medications taken by the lactating mother
- Identify, assess, and record any new or ongoing AEs or SAEs.

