4.3.2.2. If SFU conducted in person

Clinical assessments

- Identify, assess, and record any new or ongoing AEs or SAEs
- Record concomitant medications ([Section 7.7](#)). For patients who are being breast fed, record all medications taken by the lactating mother
- Record weight
- Record vital signs (heart rate/pulse, blood pressure, respiratory rate, temperature) and oxygen saturation; record highest and lowest daily temperature measurements.

Laboratory assessments

- If clinically indicated, obtain blood samples for CBC with differential and chemistry panel (see Laboratory Manual).

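### The telephone Safety Follow-up rule joins its conditions with *or*, so the condition on AEs ongoing at TOC has no effect and those infants can miss the last weight, vital signs and oxygen saturation

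*Protocol*

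**What the plan says.** Protocol 4.3.2 prefers an in-person SFU but allows a call. Protocol Table 1, footnote d, opens the rule with the first two conditions: "The SFU may be conducted via telephone for any patient who has not experienced clinical relapse, did not have ongoing AEs or SAEs at TOC". The second and third conditions, with the connector between them, read in 4.3.2: "did not have ongoing AEs or SAEs at TOC, or did not develop AEs or SAEs since TOC". SAP Table 1, footnote d, repeats the rule in the same words.

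The next sentence of 4.3.2 sets out who must come in person: "If symptoms of relapse or new AEs or SAEs are noted, or at the discretion of the investigator, the patient should be immediately scheduled".

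The two modes collect different data:

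- **Telephone (protocol 4.3.2.1):** concomitant medications, including the mother's if the infant is breast fed, and adverse events: "Identify, assess, and record any new or ongoing AEs or SAEs".
- **In person (protocol 4.3.2.2 and Table 1, footnote d):** the same, and in addition "If the visit is in-person, weight, vital signs and oxygen saturation should be recorded". Laboratory work is conditional even then: "If clinically indicated, obtain blood samples for CBC with differential and chemistry panel".

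Under protocol 3.9, AEs unresolved at the infant's last AE assessment are "followed up by the investigator for as long as medically indicated, but without further recording in the CRF".

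**The concern.** A condition about AEs still open at TOC can have only one purpose in this rule: to have those infants seen rather than telephoned. Joined by *or*, it does not do that. An infant who has not relapsed already qualifies for a call through the first condition, whatever was open at TOC.

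Safety is the primary objective and the SFU is its last scheduled assessment. If a site applies the sentence as it stands, an infant with a known unresolved event can leave the study with no final weight, vital signs or oxygen saturation on record. SAP 3.1.1 states that missing safety data are not imputed, so those values are simply absent from the summaries and listings planned in SAP 4.2.6.3.

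**Working it through.** The plan gives no figure to reproduce. The check is one of logic.

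**Inputs.** Let R = clinical relapse, O = an AE or SAE ongoing at TOC, N = an AE or SAE that developed since TOC. Each is yes or no, so there are 2 × 2 × 2 = 8 combinations.

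**Rules.**

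- *Or* (as written): a call is allowed if R is absent, or O is absent, or N is absent. It is refused only when all three are present.
- *And* (cumulative): a call is allowed only if all three are absent.
- Calling-in sentence: an in-person visit if R or N is present. Symptoms of relapse are treated here as R. Investigator discretion is left aside because it can apply to any row.

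| R | O | N | Call under *or* | Call under *and* | Called in by next sentence | Left for a call, *or* | Left for a call, *and* |
|---|---|---|---|---|---|---|---|
| no | no | no | yes | yes | no | **yes** | **yes** |
| no | yes | no | yes | no | no | **yes** | **no** |
| no | no | yes | yes | no | yes | no | no |
| no | yes | yes | yes | no | yes | no | no |
| yes | no | no | yes | no | yes | no | no |
| yes | yes | no | yes | no | yes | no | no |
| yes | no | yes | yes | no | yes | no | no |
| yes | yes | yes | no | no | yes | no | no |

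**Results.**

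1. Before the calling-in sentence, 7 of 8 combinations qualify under *or* and 1 of 8 under *and*.
2. After it, 2 remain under *or* and 1 under *and*. The two readings differ in one row: no relapse, event ongoing at TOC, no new event.
3. Every infant not called in has R absent, so the *or* rule is already met whatever the value of O. Deleting the ongoing-event condition would change no infant's visit mode.

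**What that row loses.** Comparing 4.3.2.1 with 4.3.2.2, the certain loss is one weight, one set of vital signs and one oxygen saturation reading. CBC and chemistry are not mandatory at an in-person SFU, so a call removes the occasion for them, not a required test.

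**Scale.** The documents give no expected number of infants with an event open at TOC. One such infant is 1/24 = 4.2% of the planned total, or 1/8 = 12.5% of a cohort. These are weights per infant, not estimates of how often it would happen.

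**The case against.** The strongest case on the other side is that this is loose drafting with little consequence. Much of it stands.

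- **Intent.** Taken alone, the *or* rule would allow a call even to a relapsed infant, so the authors probably meant the list to be cumulative. That is likely, but no passage says so, and the same connector appears in all three places.
- **Other routes to an examination.** A reader might infer that nothing could bring such an infant in. The documents do not support that. Protocol 4.3.2 prefers an in-person visit and allows one at the investigator's discretion. Section 4 allows unplanned visits for the subject's well-being. Section 6.4.1 brings potential drug-induced liver injury cases back to the site for laboratory tests and physical assessment. What is missing is a mandatory trigger.
- **SAEs.** A reader might infer that the record of an unresolved SAE ends with the call. It does not. Protocol 6.1 requires the investigator to pursue the outcome of each event and to send new SAE information within 24 hours. Section 6.1.4.1 continues SAE follow-up until resolution or stabilisation with the sponsor's agreement. For non-serious AEs, 6.1.4.2 says only that follow-up may be required, and 3.9 ends CRF recording, so the gap lies mainly there.
- **Worsening events.** The AE definition in SAP 3.1.1.1 includes deterioration of an existing condition, so a worsening event may count as new and trigger a visit. An event that is stable or slowly resolving would not.
- **Primary outcome.** The primary measures are AEs, SAEs, deaths and discontinuations due to AEs. The call records new and ongoing events, and apart from fatal outcomes the AE tables in SAP 4.2.6.1 do not report resolution. Those tables are essentially unaffected.

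None of this gives the ongoing-event condition any effect.

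**Conclusion.** The rule is wrong as written, with minor severity. Read literally, and after the calling-in sentence, an infant whose AE or SAE was still ongoing at TOC, with no relapse and no new event, may have the SFU by telephone unless the investigator decides otherwise. The certain loss for each such infant is the SFU weight, vital signs and oxygen saturation. The loss falls mainly on infants with ongoing non-serious AEs, whose later course is not entered in the CRF.

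The conclusion assumes that sites apply the sentence literally, that an unchanged event from TOC is not counted as new, and that discretion is not used. The documents do not show how any site read the rule or how many infants it would affect. The count of 7 in 8 describes logical combinations and should not be read as a share of infants. No sample size, power or error rate is touched.

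**What to change.** In protocol 4.3.2, protocol Table 1 footnote d and SAP Table 1 footnote d, make the three conditions cumulative: a telephone SFU only for a patient with no clinical relapse, **and** no AE or SAE ongoing at TOC, **and** no AE or SAE since TOC. Each condition then has effect, and the text agrees with the protocol's preference for an in-person SFU.

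The sentence that calls infants in needs no change. Once the conditions are cumulative, an infant with an event open at TOC no longer qualifies for a call.

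The cost is a wording edit in three places and a few more infants attending in person. That number cannot be given from the documents.
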